10.3.1 Extent of Exposure

Extent of exposure and compliance derived from the subject diary eCRF and "Date of last study drug intake" in the End Of Treatment CRF form will be summarized as continuous for the following:

- Date of last dose of study drug, defined as the "Date of last study drug intake" in the End Of Treatment CRF form, or if missing will be replaced with the date of last non-zero drug intake in the subject diary.
- Treatment duration (weeks), defined as (date of last dose of study drug – date of first dose + 1)/7.
- Number of completed 28-day cycles, defined as the integer value of floor(treatment duration in days/28). (Note: Report only the median, quartiles, min and max.)
- Cumulative dose (mg), defined as (total number of tablets taken during the study)*20 mg. Note: In the case of incomplete diary data over the treatment duration of the subject, the days

with missing tablet counts will be assumed to have a zero tablet count in the calculation of cumulative dose over the treatment duration.

- Planned cumulative dose (mg), defined as (treatment duration in days)*80 mg. For any period where there is a dose reduction this will be multiplied by 60 mg. Note: This quantity is not summarized, but only used in calculation of treatment compliance.

- Dose intensity (mg/day), defined as

$$\text{Cumulative dose (mg)} / \text{Treatment duration (days)}$$

- Treatment compliance (a.k.a. relative dose intensity) (%), defined as

$$(\text{Cumulative dose (mg)} / \text{Planned cumulative dose (mg)}) * 100$$

- Treatment compliance for first 4 cycles (%), defined as

$$(\text{Cumulative dose (mg) for the period where dose date} - \text{treatment start date} \leq 112 / \text{planned cumulative dose for first 4 cycles (112 multiplied by 80 mg. For any period where there is a dose reduction this will be multiplied by 60 mg.)})$$

Number (%) of patients will be presented for:

- Treatment compliance (≥ 75 , $< 75\%$)
- Treatment compliance for first 4 cycles (≥ 75 , $< 75\%$)
- Number of dose reductions: 0 or 1 dose reduction. (Note: Patients will be permanently discontinued if a second reduction is necessary and thus having > 1 dose reduction should not occur according to protocol procedures. If the > 1 dose reduction category occurs it will additionally be displayed).

A study day between study drug first dose day and last dose day (or last dose at data cut off) is considered a temporary interruption if the number of tablets taken is 0 or missing as recorded in the subject diary eCRF. An episode of temporary interruption is defined as a run of consecutive days with temporary interruption that are flanked before and after by a day with > 0 number of tablets taken. Patients can have multiple episodes of temporary interruption. Temporary interruptions based on the subject diary eCRF will be summarized as follows:

- Number (%) of patients with at least one interruption.
- Number of episodes of interruption per patient presented as continuous and as categories (0, 1, 2, > 2).
- Maximum duration of an interruption episode (days) presented as continuous and as categories (0, ≥ 1 to < 5 , ≥ 5 to < 7 , ≥ 7 to < 14 , ≥ 14 days). This is a summary of the episode with the maximum number of consecutive days with interruption.
- Cumulative duration of interruption days presented as continuous and as categories (0, ≥ 1 to < 5 , ≥ 5 to < 7 , ≥ 7 to < 14 , ≥ 14 days). This is the total interruption days summed over all episodes.

Temporary interruptions due to AE will be defined using the AE CRF data:

- Number (%) of patients with at least one interruption due to AE, defined as having at least 1 TEAE with “Action taken with Study Drug” = Temporarily Interrupted.
- Number of interruptions due to AE per patient presented as continuous and as categories (0, 1, 2, > 2), defined as counting unique start dates of TEAEs with “Action taken with Study Drug” = Temporarily Interrupted. (Note: Counting only unique start dates ensures we do not double-count AEs that are part of the same interruption episode.)

Subject diary information will be presented in a data listing.

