## 7.6. Method of Administration and Compliance

Debio 1347 tablets will be administered orally at the dose of 80 mg once daily from Day 1 to Day 28 in 28-day cycles (see study plan in Section 8.3) until occurrence of any of the criteria described in Section 8.4.1.

Debio 1347 will mostly be self-administered by subjects at home and should be taken at approximately the same time each day as follows:

1. Debio 1347 must be taken early in the morning. Subjects must fast (only water permitted freely) for 4 hours before and 2 hours after intake.
2. If a dose is not administered for reasons other than toxicity, the subject may take the dose later in the day but no later than 6 hours after normal intake time. If the delay exceeds 6 hours, the subject must wait until the next scheduled administration.
3. If the subject vomits after Debio 1347 intake, another dose should not be administered, rather wait until the next scheduled dose.

Subjects will also be instructed by study staff on how to take Debio 1347.

Dose adjustments are permitted as described in Section 5.3.

Subject compliance will be verified by a) means of a diary card or equivalent electronic tool to be filled out after each dose when taken at home and b) direct visual supervision at dosing by the Investigator or designee when the drug is administered at the study site. Compliance will be checked by the Investigator or designee at each study visit and the number of returned tablets and date will be recorded when applicable.

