7.4 Per Protocol Population (PP)

The per protocol (PP) population consists of all subjects in the ITT population who have undergone radiographic assessment at baseline (i.e., tumor assessment screening visit), received at least one dose of study drug, had both baseline and post-baseline disease and had no critical protocol deviation that may have an impact on efficacy endpoints.

Having radiographic assessment at baseline and baseline disease is considered met if inclusion criterion 7 (having measurable disease according to RECIST 1.1 at baseline) is Yes.

Having post-baseline disease is clarified as requiring at least 1 post-baseline disease assessment.

Critical protocol deviations that may have an impact on efficacy endpoints are defined as (also see Section 13.6):

- Violation of any inclusion/exclusion criteria at entry.
- Actual cumulative dose below 75% of planned cumulative dose from date of first dose to date of end of cycle 4 or date of treatment discontinuation, whichever occurs first.
- Subject data indicate a major protocol deviation other than the criteria defined above, that potentially affects efficacy assessment and is identified prior to database lock.

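### The SAP reports missing diary days as missed doses and interruptions, which distorts the exposure tables and, where diaries are lost in blocks, Per Protocol membership

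*SAP*

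**What the plan says.** SAP 10.3.1 builds exposure from the subject diary and from the last-dose date on the End of Treatment form.

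- **Numerator.** Where the diary is incomplete, days "with missing tablet counts will be assumed to have a zero tablet count in the calculation of cumulative dose". Dose intensity and treatment compliance both use this cumulative dose.
- **Denominator.** "Planned cumulative dose (mg), defined as (treatment duration in days)*80 mg", with 60 mg for any dose-reduced period. For the first four cycles it is "planned cumulative dose for first 4 cycles (112 multiplied by 80 mg", again with 60 mg where reduced. Neither removes blank days.
- **Interruptions.** A day between first and last dose is "considered a temporary interruption if the number of tablets taken is 0 or missing as recorded in the subject diary eCRF". An episode is a run of such days "flanked before and after by a day with > 0 number of tablets taken". Interruptions due to adverse events are derived separately, from the AE form.
- **PP population.** SAP 7.4 lists as a critical deviation "Actual cumulative dose below 75% of planned cumulative dose from date of first dose to date of end of cycle 4", or to discontinuation if earlier. SAP 10.1.1 tabulates this exclusion reason as compliance below 75%.
- **Other source.** Protocol 7.6 relies on the diary for home dosing, on direct observation for dosing at the site, and adds that "the number of returned tablets and date will be recorded when applicable". The SAP makes no use of the returned counts.

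Protocol 11.5.2 leaves missing data unimputed unless stated otherwise. The SAP does state otherwise here, but gives no justification, minimum diary completeness, sensitivity analysis or separate category for missing diary days.

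**The concern.** A blank diary day says that intake is unknown. Setting it to zero picks the lowest possible value, and leaving it in the denominator turns the gap into non-compliance. The error has one direction: exposure and compliance fall, and diary-based interruptions rise. A reader of the exposure tables could take poor record keeping for poor tolerability. Through the 75% criterion, the supportive PP analyses of ORR, DOR, DCR and PFS could also lose subjects because of paperwork rather than drug intake.

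**Working it through.** **Inputs.** 28-day cycles and 80 mg daily (Protocol 5.2); the zero rule, the denominators and the interruption definitions (SAP 10.3.1); the 75% cut-off (SAP 7.4). The documents give no rate of missing diary days, so a range is assumed.

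**Plan's own figure.** 4 × 28 = 112 days, as in SAP 10.3.1. 112 × 80 mg = 8960 mg, and 75% of that is 6720 mg.

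**1. Full true intake, no dose reduction, *m* blank days out of *D*.** Compliance under the SAP is (*D* − *m*)/*D*; exclusion requires a value below 0.75. *D* = 51 is the Phase I median duration of 7.3 weeks (Protocol 3.3.2; 7.3 × 7 ≈ 51), used for context only.

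| Window *D* (days) | Fewest blank days that exclude | Compliance then | Compliance with one 28-day diary lost |
|---|---|---|---|
| 28 | 8 | 20/28 = 71.4% | 0/28 = 0% |
| 51 | 13 | 38/51 = 74.5% | 23/51 = 45.1% |
| 56 | 15 | 41/56 = 73.2% | 28/56 = 50.0% |
| 84 | 22 | 62/84 = 73.8% | 56/84 = 66.7% |
| 112 | 29 | 83/112 = 74.1% | 84/112 = 75.0% (not excluded) |

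**2. Incomplete true intake.** With adherence *a* on recorded days, exclusion needs *m* > *D*(1 − 0.75/*a*).

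- *a* = 0.90: 112 × 0.1667 = 18.7, so 19 days; 56 × 0.1667 = 9.3, so 10 days.
- *a* = 0.80: 112 × 0.0625 = 7.0, so 8 days; 56 × 0.0625 = 3.5, so 4 days.

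**3. False interruption episodes.** Assume full intake, first and last dosing days recorded, and each other day blank independently with probability *q*. The chance of at least one false episode is 1 − (1 − *q*)^(*D* − 2).

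| Assumed *q* | 56 days | 112 days |
|---|---|---|
| 0.5% | 24% | 42% |
| 1% | 42% | 67% |
| 2% | 66% | 89% |
| 5% | 94% | 99.6% |

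**4. Same scattered blanks, PP exclusion at full intake.** The binomial probability that more than a quarter of the days are blank is largest at *q* = 5% and *D* = 56, where it is 7.0 × 10⁻⁸. Scattered blanks therefore distort the interruption table but do not remove fully adherent subjects from PP.

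**5. After Amendment 2.** SAP 10.3 says that only AEs, SAEs and AESIs are then entered in the eCRF, while the last-dose date still comes from the End of Treatment form. If diary entry stopped, later treated days would count as zero: diary to day 112 and last dose on day 168 gives 112/168 = 66.7% overall compliance. The documents do not say whether diary entry continued.

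**6. Compliance over documented days.** At full intake this is (*D* − *m*)/(*D* − *m*) = 100% for any *m* < *D*, with no false interruption.

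**The case against.** The best defence is that a blank day is no proof of intake either. A subject who stops both dosing and recording would score 100% if blank days were simply dropped, so counting them as zero is a disclosed, cautious convention for compliance. Returned-tablet counts are a weak substitute: they are recorded only when applicable, cannot date a missed dose, and treat unreturned tablets as taken. Nothing shows that dispensed and returned counts are in the analysis database. The SAP also lists diary data, tabulates and lists reasons for PP exclusion, and reviews deviations before database lock.

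Much of this stands. Returned counts can serve as a check but not as a replacement, and the zero rule deserves to stay as a sensitivity analysis. It does not rescue the main tables: what is cautious for compliance overstates interruptions, and a listing does not correct a summary.

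Three stronger readings are tempting, and the documents do not support them.

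- *Lost diaries routinely turn compliant subjects into PP exclusions.* At full intake more than 25% of the window must be blank, and one lost 28-day diary in 112 days gives exactly 75.0%, which is not below the cut-off. SAP 7.4 also does not cite the zero rule, which is worded for cumulative dose over the whole treatment duration. Its use in the PP window is a reasonable inference because no other definition exists.
- *The trial's conclusion is at risk.* ITT is primary. On the unconfirmed counts at the second IDMC meeting (SAP Table 6: 3/63 central, 4/63 local), passing 15% while keeping every responder would mean dropping 44 non-responders (3/19 = 15.8%) or 37 (4/26 = 15.4%).
- *Any lost diary shows up as a long interruption.* A gap at the end of treatment has no later dosing day to flank it, so it forms no episode.

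**Conclusion.** The concern holds within limits. SAP 10.3.1 reports undocumented days as non-intake, which biases dose intensity and compliance downward and diary-based interruptions upward. The interruption table is the most sensitive output: one flanked blank day is enough, and at the assumed 0.5% to 5% of days blank, 24% to 94% of perfectly adherent subjects over 56 days would show a false episode. PP membership is affected only by block loss of diaries or when true adherence is already near 75%, and only if the zero rule is applied in the PP window.

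The primary ITT ORR and the AE-based interruptions do not change. The affected outputs are the exposure tables, the diary-based interruption tables and the supportive PP analyses. The last are not negligible descriptively: with three unconfirmed central responses among 63 subjects, one wrongly excluded responder would be a third of them. How large the effect really is depends on diary completeness, which the documents do not report.

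**What to change.** In SAP 10.3.1, classify each day from first to last dose as recorded intake, recorded zero or missing. Then:

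- base the main interruption table on recorded zeros plus days covered by an AE whose action was a temporary interruption, and tabulate missing diary days separately. The SAP describes AE start dates rather than interruption dates, so it must state how days are matched;
- compute dose intensity and compliance over documented days, checked against returned-tablet counts where these were recorded;
- state in SAP 7.4 that missing diary days alone do not exclude a subject from PP, and which cumulative-dose rule applies in that window;
- keep the current zero rule as a sensitivity analysis;
- state whether diary entry continued after Amendment 2.

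A neighbouring conflict should be reconciled in the same edit. The first-four-cycle formula in SAP 10.3.1 has a fixed 112-day denominator, while SAP 7.4 stops at discontinuation. Under the fixed denominator a subject with full intake who stops at day 56 scores 56/112 = 50% with no diary day missing.

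The cost is SAP wording and some extra programming. Compliance over documented days may be slightly optimistic if blank days include true missed doses; the zero-imputed analysis gives the lower bound.

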9.2 Dates, Times and Days

Study day is defined as:

- (Date of event) – (Date of first dose of study drug) + 1, if the event is on or after the date of first dose;
- (Date of event) – (Date of first dose of study drug), if the event is before the date of first dose.

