10.1 Disposition of Subjects, Demographic and Baseline Data

10.1.1 Subject Disposition

Number (%) of patients will be presented by total patients only for All Screened Subjects, in the following:

- Screened (patients with informed consent) (number only)
- Screened but not enrolled and by reason for not enrolling

Number of patients will be presented for:

- Enrolled but not treated
- Treated

Number (% , calculated using denominator of treated patients) will be presented for

- End of treatment status (ongoing at data cut-off, discontinued) and by reason for treatment discontinuation
- End of study status (ongoing at data cut-off, discontinued) with reason for study discontinuation
- Subject in ITT, mITT, Safety, PP, PK population.

Number (%) of patients will be summarized in each analysis population (ITT, mITT, PP, SAF and PKP). Reasons for exclusion from PP will be provided:

- No measurable disease at baseline (inclusion criterion 7)
- No post-baseline disease assessment
- Violation of eligibility criteria at entry
- Treatment compliance <75%
- Other major protocol deviation that potentially affects efficacy assessment

Subjects per country and sites will be tabulated for the ITT, mITT and PP.

All subject disposition data will be presented in data-listings. Screening failure and reasons will be listed separately. Reason of exclusion from each analysis population will be listed.

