13. Subjects with a known history of uncontrolled or unstable angina or myocardial infarction within the last 6 months, unstable cardiac arrhythmias despite treatment (subjects with a history of atrial fibrillation stabilized under treatment are allowed), unexplained recurrent syncope, family history of sudden death from cardiac-related causes, congestive heart failure greater than New York Heart Association (NYHA) class II, uncontrolled diabetes, uncontrolled psychiatric disorders, severe ongoing infections or any other medical condition that might be aggravated by the treatment on evaluation.		
14. Prolongation of QTcF interval to greater than 480 msec.		
15. History of congenital long QT syndrome		
16. History of another malignancy other than the primary tumor within the last 2 years, with the exception of completely resected basal or squamous cell skin cancer or any successfully treated in-situ carcinoma, or clinically insignificant prostate cancer without any treatment intent (either treated or on active surveillance/watchful waiting). Other cancers within the last 2 years that are considered clinically insignificant by the treating physician should be discussed with the study Sponsor to assess eligibility.		
17. Known infection requiring the systemic use of, for example, an antibiotic or antiviral agent.		

18. Uncontrolled intercurrent illness or psychiatric illness/social situations that would limit compliance with study requirements.		
19. If female, pregnant or breast feeding.		
20. Unable to swallow and retain oral medications.		
21. Known contraindication to enhanced magnetic resonance imaging (MRI) and/or computerised tomography (CT) scan.		
Additional criteria		
Actual cumulative dose below 75% of planned cumulative dose from date of first dose to date of end of cycle 4 or date of treatment discontinuation, whichever occurs first;		
Major protocol deviations that may have an impact on efficacy endpoints.		

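### SAP 10.3.1 divides first-four-cycle compliance by a fixed 112 days, so a fully adherent subject at 80 mg who stops before day 84 is counted as below 75%

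*SAP*

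**What the plan says.** SAP 10.3.1 (Extent of Exposure) defines two compliance percentages, and both are tabulated as ≥75% or <75%.

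- **Overall compliance.** The denominator follows time on drug: "Planned cumulative dose (mg), defined as (treatment duration in days)*80 mg", with 60 mg for reduced periods.
- **First-four-cycle compliance.** The numerator is "Cumulative dose (mg) for the period where dose date" minus treatment start date is at most 112. The denominator is "planned cumulative dose for first 4 cycles (112 multiplied by 80 mg", again with 60 mg for reduced periods. No other adjustment is given.
- **Diary gaps.** In the cumulative dose, days "with missing tablet counts will be assumed to have a zero tablet count".

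SAP 7.4 (Per Protocol Population) excludes subjects whose cumulative dose is below 75% of plan, over a window from first dose to "end of cycle 4 or date of treatment discontinuation, whichever occurs first". The additional criteria in SAP 13.6 repeat that window. SAP 10.1.1 labels the matching exclusion reason only as "Treatment compliance <75", followed by a percent sign.

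**The concern.** A compliance percentage should compare what a subject took with what that subject was due to take. With the denominator held at 112 days, days after treatment has ended count as planned dosing days on which nothing was taken. Early stopping, usually for progression or toxicity, is then reported as non-compliance.

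Two rows in the same section, both called compliance and both cut at 75%, can put the same subject in opposite categories. The row also fails to match the four-cycle, 75% rule that the SAP sets elsewhere. At stake is the correctness of one set of ≥75/<75% counts in the Safety population's exposure summary, and a reader's ability to separate missed doses from short treatment.

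**Working it through.** **Inputs**

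- 80 mg once daily in 28-day cycles (SAP 4.2).
- Treatment duration = last dose date − first dose date + 1 (SAP 10.3.1).
- 75% cut-off (SAP 10.3.1, 7.4, 13.6).
- Study-day convention: date difference plus one, "Date of first dose of study drug) + 1, if the event is on or after the date of first dose" (SAP 9.2).

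**The plan's own figure.** 4 × 28 = 112 days, and 112 × 80 mg = 8,960 mg. This reproduces the SAP's denominator. The number is right for four completed cycles; the fault is in applying it to everyone.

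**Test case.** Take an unreduced subject with a complete diary, every tablet taken, and last dose on day k ≤ 112.

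- First four cycles: 80k / 8,960 = k/112.
- Overall: 80k / 80k = 100%.
- SAP 7.4/13.6 if discontinuation is dated at the last dose: k/k = 100%.
- SAP 7.4/13.6 if discontinuation is dated 21 days later: k/(k + 21).

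The last line is needed because the SAP does not say that the discontinuation date is the last-dose date, and Protocol 8.2.7 equates discontinuation with the EOT visit. The 21 days is an illustrative assumption, borrowed from the recovery limit in Protocol Table 5-1. Nothing in the documents says that discontinuation is dated that way.

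| Last dose, day k | 10.3.1 first four cycles | 10.3.1 overall | 7.4, no lag | 7.4, 21-day lag |
|---|---|---|---|---|
| 28 | 28/112 = 25.0% | 100% | 100% | 28/49 = 57.1% |
| 56 | 56/112 = 50.0% | 100% | 100% | 56/77 = 72.7% |
| 62 | 62/112 = 55.4% | 100% | 100% | 62/83 = 74.7% |
| 63 | 63/112 = 56.3% | 100% | 100% | 63/84 = 75.0% |
| 83 | 83/112 = 74.1% | 100% | 100% | 83/104 = 79.8% |
| 84 | 84/112 = 75.0% | 100% | 100% | 84/105 = 80.0% |

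**Threshold.** k/112 ≥ 0.75 requires k ≥ 0.75 × 112 = 84 days, or 12 weeks. Day 83 is tabulated as <75% and day 84 as ≥75%.

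**Against SAP 7.4.** k/(k + 21) ≥ 0.75 when k ≥ 63. For any lag of up to 21 days, last doses from day 63 to day 83 satisfy 7.4 but fail 10.3.1, so the disagreement does not depend on how discontinuation is dated.

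**Numerator window.** Date differences 0 to 112 are study days 1 to 113, one more than four cycles. A fully adherent subject treated beyond day 112 scores 113/112 = 100.9%.

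**How many subjects.** The documents do not give the number affected. There are two reference points, both from Protocol 3.3.2 and both assumptions when applied to unreduced subjects here:

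- If durations resemble the whole Phase I escalation, the median of 7.3 weeks is 7.3 × 7 ≈ 51 days, which scores 51/112 = 45.5%. At least half would be tabulated as <75% with perfect adherence.
- If durations resemble the 10 fusion-positive Phase I subjects at ≥60 mg/day, 3 + 5 = 8 had disease control. If the 24 to 47 weeks reported for subjects with disease control applies to those 8, the shortest is 24 × 7 = 168 days, above 84. At most 2 of 10 would be affected.

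**The case against.** The strongest reply is that nothing is miscalculated. Four cycles are 112 days, and dose received against a fixed planned course is a coherent exposure measure. SAP 10.3.1 itself treats overall compliance as relative dose intensity. On that view, 100% overall with 25% of the four-cycle plan simply describes a subject who stopped early, and treatment duration, completed cycles and dose intensity in the same section make that visible. Under the proposed change the row would equal overall compliance for everyone whose last dose is by day 112. The Phase I durations also come from a different dose range and a less selected population, so frequency is uncertain.

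Much of this stands as a limit on importance: the row is descriptive, its neighbours help the reader, and the number affected is unknown. It does not rescue the definition. The row is named compliance and split at the compliance threshold, and time on drug already has its own rows. The SAP's other four-cycle 75% rule is truncated.

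A second objection is partly right. Truncating at last dose does not guarantee agreement with SAP 7.4. With a 21-day lag and last dose on day 56, the repaired row gives 100% and 7.4 gives 72.7%. That remaining gap comes from the undefined discontinuation date in 7.4.

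**Conclusion.** The definition is wrong as written, and the consequence is minor. For unreduced subjects with complete diaries and full adherence, every last dose before day 84 is tabulated as <75%, with scores down to 25.0% at day 28, against 100% in the adjacent overall row. The 113-day numerator is a separate and trivial slip (at most 100.9% in this case).

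The ITT response rate is unaffected. The PP rule in SAP 7.4 and 13.6 stands as worded, and SAP 10.3.1 does not claim to drive it. The day-84 boundary and the conflict with the overall row follow from the SAP's formulas for the stated test case. Only the 21-day lag and the Phase I comparisons are assumptions, and the result does not rest on either.

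**What to change.** - **SAP 10.3.1, denominator:** compute the planned dose for the first four cycles over min(112, last dose date − first dose date + 1) days, keeping 60 mg for reduced periods. The test subject then scores 100% for every last dose from day 1 to day 112, in line with the overall row.
- **SAP 10.3.1, numerator:** restrict to a date difference of at most 111 (study days 1 to 112).
- **SAP 10.1.1:** add a phrase saying that the compliance exclusion reason is the dose criterion of SAP 7.4. This is a clarification only.
- **SAP 7.4 and 13.6:** leave as worded. Do not use the 10.3.1 variable to decide PP membership unless the SAP first states that the discontinuation date is the date of last dose.

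The cost is one corrected formula, one clarifying phrase and reprogramming of one descriptive variable. No new data are needed and the PP rule does not change.

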4.2 Study Treatments

Subjects will receive Debio 1347 tablets at the dose of 80 mg QD from Day 1 to Day 28 in 28-day cycles until occurrence of any of the criteria described in the protocol requiring treatment discontinuation.

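### SAP 10.3.1: first-four-cycle compliance sums dose over 113 days but divides by 112 planned days, inflating the figure by up to 0.9 percentage points for subjects dosed on Day 113

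*SAP*

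**What the plan says.** SAP 4.2 gives Debio 1347 "at the dose of 80 mg QD from Day 1 to Day 28 in 28-day cycles", so four cycles are 4 × 28 = 112 days. SAP 9.2 numbers days from the first dose: the date difference is increased by "1, if the event is on or after the date of first dose". The first-dose date is therefore Day 1, not Day 0.

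SAP 10.3.1 builds the four-cycle measure from two parts:

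- Numerator: "Cumulative dose (mg) for the period where dose date" minus treatment start date is less than or equal to 112. Nothing is added to the difference.
- Denominator: "planned cumulative dose for first 4 cycles (112 multiplied by 80 mg", with the adjustment "For any period where there is a dose reduction this will be multiplied by 60 mg".

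The result is tabulated as at least 75% or below 75%. In the same section, treatment duration is last dose date minus first dose date plus 1, so overall compliance counts both end days.

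SAP 7.4 uses a 75% limit as a critical deviation for the Per Protocol population, in its own words: "Actual cumulative dose below 75% of planned cumulative dose from date of first dose to date of end of cycle 4", or to treatment discontinuation if that is earlier.

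**The concern.** The two halves of one ratio cover different numbers of days. The numerator admits one dose that belongs to Cycle 5, and the denominator plans no dose for that day. A perfect record then exceeds 100%, and it disagrees with overall compliance in the same section, which would read 100.0% for the same subject.

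What is at stake is small but visible. The continuous summary of this variable moves upward for longer-treated subjects. A subject just under the 75% limit can also move to the other side of it in the exposure table.

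**Working it through.** **Inputs.** Cycle length 28 days and dose 80 mg once daily (SAP 4.2); day numbering (SAP 9.2); numerator limit 112, planned dose, 20 mg tablets and the 75% cut (SAP 10.3.1).

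**The plan's own denominator.** 4 × 28 = 112 days; 112 × 80 mg = 8,960 mg, or 112 × 4 = 448 tablets. This agrees with the SAP.

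**Numerator days as written.** Differences 0, 1, …, 112 are 113 dates. By SAP 9.2, difference 111 is Day 112 (the end of Cycle 4) and difference 112 is Day 113.

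| Window | Days counted |
|---|---|
| difference ≤ 112 (as written) | 113 |
| difference ≤ 111 | 112 |
| study day ≤ 112 | 112 |

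**Full compliance at 80 mg, dosed through Day 113.** 113 × 80 = 9,040 mg; 9,040/8,960 = 100.9%. With the limit at 111: 8,960/8,960 = 100.0%.

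**Size of the shift.** One 80 mg dose adds 80/8,960 = 0.89 percentage points.

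**After a reduction to 60 mg that is still in force on Day 113.**

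| Reduced from | Numerator / denominator (mg) | Full compliance reads |
|---|---|---|
| Day 29 | 7,340 / 7,280 | 100.8% |
| Day 112 | 9,000 / 8,940 | 100.7% |

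**At the 75% limit (80 mg throughout).** 75% of 448 tablets is 336.

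| Tablets, Days 1–112 | True % | With 4 tablets on Day 113 | Class as written |
|---|---|---|---|
| 331 | 73.9 | 335/448 = 74.8 | < 75% |
| 332 | 74.1 | 336/448 = 75.0 | ≥ 75% |
| 335 | 74.8 | 339/448 = 75.7 | ≥ 75% |
| 336 | 75.0 | 340/448 = 75.9 | ≥ 75% |

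In whole doses, 83/112 = 74.1% becomes 84/112 = 75.0%. The affected band is 332 to 335 tablets. At 332 all four tablets on Day 113 are needed to cross (336 − 332 = 4); at 335 one is enough.

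**Not dosed on Day 113.** The extra date contributes 0 mg and the figure is unchanged.

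**The case against.** The case for leaving this alone has four parts.

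1. **The Per Protocol population is not shown to be wrong.** A reader might infer that the faulty window decides Per Protocol membership because both use 75%. The documents do not support that. SAP 7.4, repeated in SAP 13.6, states a window ending at Cycle 4 or discontinuation, and that window excludes Day 113. SAP 10.1.1 lists compliance below 75% as a reason for exclusion but does not say which compliance variable is meant. Membership is affected only if the flag is programmed from the 10.3.1 variable. That is possible, since 10.3.1 holds the only explicit four-cycle formula, but it is not stated. Per Protocol is also only a supportive population (SAP 10.2). This objection stands.

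2. **Few subjects can be affected.** A reader might also take the 0.9 points as a shift for everyone. It is zero for anyone not dosed on Day 113, the first day of week 17. In the Phase I study, median treatment was 7.3 weeks overall, though 34 weeks in subjects with disease control (Protocol 3.3.2). Some subjects would pass Day 113, but nothing shows that any falls in the four-tablet band. This stands too: the 74.1% case is a boundary illustration, not an observed error.

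3. **The output is descriptive.** The variable does not enter the response rate in the primary ITT analysis. This is correct.

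4. **Other features of the variable matter more.** Missing diary days count as zero tablets, and the 112-day denominator is not cut off at discontinuation, so a fully compliant subject who stops at Day 56 reads 56/112 = 50%. These are separate matters. The uncapped denominator lowers the figure for early stoppers, while the extra day raises it for subjects treated past Cycle 4. Correcting one leaves the other.

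None of this removes the mismatch. No other section corrects the window, and the day-count conventions in SAP 9.2 and in the duration formula of 10.3.1 both go against it.

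**Conclusion.** The formula is wrong as written: 113 days of dose over 112 days of plan. For subjects dosed on Day 113 it overstates first-four-cycle compliance by up to 0.9 percentage points, usually slightly less after a reduction to 60 mg. It can move a subject at 80 mg with 332 to 335 of 448 tablets into the upper class of the exposure table. All other subjects are untouched. Per Protocol membership is at risk only if its criterion is coded from this variable. The point is minor and does not bear on the primary result.

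This rests on three assumptions:

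- The printed limit is a non-strict inequality at 112; a strict one would give 112 days and remove the point.
- Treatment start date is the date of first dose.
- A subject reduced to 60 mg is still on 60 mg on Day 113. Protocol 5.3.1 allows a return to 80 mg after discussion. If that happened exactly on Day 113 after a reduction from Day 29, the shift would be 80/7,280 = 1.1 points, a rare exception to the 0.9 ceiling.

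**What to change.** In SAP 10.3.1, change the numerator window to dose date minus treatment start date ≤ 111, or equivalently study days 1 to 112 under SAP 9.2. Full compliance then reads 100.0%, and 83 of 112 doses reads 74.1% and is classed below 75%.

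In the same edit, state in SAP 7.4 or 10.1.1 which variable supplies the Per Protocol compliance flag, and that its window ends at Cycle 4 or discontinuation as 7.4 already says.

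The cost is one number in the SAP and the matching line of code, plus one clarifying sentence. No data collection or clinical rule changes. The only visible effect is slightly lower compliance for subjects dosed on Day 113.
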